- We will also measure subjects resting metabolic rate, a measure of the amount of energy it takes to burn calories. While laying down subjects will wear a canopy (cover) that is connected to a special device (metabolic cart) that measures exhaled carbon dioxide (CO₂) and oxygen through indirect calorimetry. These measurements are then used to calculate the number of calories burned to determine food needs.

B. Treadmill exercise testing for cardiovascular fitness (i.e. VO2max):

- Subjects will be asked to perform a maximal treadmill exercise test in the CRC or the IFNH. The test will begin with low speed on the treadmill, and the resistance will increase gradually every 2 minutes. Subjects will be asked to go as long as you can, that is, until you feel exhausted.
- During the test, Subjects may have continuous electrocardiogram (ECG) heart monitoring and blood pressure monitoring if you are considered at risk.
- During exercise testing we will also measure subjects metabolic rate, a measure of the amount of
 energy it takes to burn calories. During exercise they will wear a facemask that is connected to a
 special device (metabolic cart) that measures your exhaled carbon dioxide (CO₂) and oxygen
 through indirect calorimetry. These measurements are then used to calculate the amount of
 calories you burn.
- During the exercise test, subjects will wear a mask over your nose and mouth. This allows us to measure how much oxygen they are using and will tell us what their fitness level is.
- The visit ends after the subject completes the exercise test. Subjects will receive the results of their test after the completion of the study.
- Subjects will also be provided with an **accelerometer** and instructions on how to use the accelerometer. The accelerometer is a small device, similar to a pedometer, which is worn on their belt and records the amount of activity performed. Data will be downloaded when the device is returned.

C. Physical Activity questionnaire

• *Minnesota Leisure Time Physical Activity:* This is a checklist of 60 physical or recreational activities subjects may have participated in over the last 12 months. This takes about 10 minutes to complete.

D. Diet logs and appetite questionnaires

Subjects will fill out a daily record of eating habits for 3 days at weeks 0, 4, 8, 12 and 16. Subjects
will also answer questions that test responses to the food eaten. This takes about 30 minutes to
complete.

E. Quality of life questionnaires

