W, and F) with the exercise physiology staff at the Loree Gymnasium or IFNH on Cook-Douglas Campus. On the remaining 2 days a week (e.g. T and Thr) subjects will be instructed to exercise on their own for half the time that they do in the supervised training sessions. These days are designed to help subjects body recover. Overall, the training program will ask subjects to exercise 5 times per week. Subjects heart rate will be monitored continuously, and subjects will be asked to exercise at an intensity near 50-55% of theiir previously measured fitness level. The amount of time subjects exercise will vary based on capacity to burn 400 kcal on supervised days and 200 kcal on unsupervised days. During the first days of training we will measure breath samples during exercise to ensure proper exercise intensity and determine how many calories from sugar and fat subjects are burning for energy. Every 4 weeks subjects will have their body weight and waist circumference measured prior to a training session. In addition to this training program subjects will be provided a placebo. The Placebo is a harmless substance that looks like the study drug, but which should have no effect. Subjects will not be able to find out if they are on the placebo or metformin (i.e. the real drug) until the study is done. Pills will be provided to the subjects by the research team as prepared by Rutgers Pharmacy in the CRC on a weekly basis (i.e. [name], CRC Pharmacy). Unused pills should be returned to our research team. If the subject's doctor needs to know whether metformin or placebo pill is prescribed due to medical reasons that directly affect their medical care, the people doing this study can find out. At weeks 0, 8 and 16, accelerometers will be provided to characterize non-exercise physical activity. Breath samples during exercise will also occur at the end of training.

HiEx + Placebo: If subjects are randomly assigned to this group, subjects will participate in exercise training just as described above. However, here the exercise training intensity based on subjects heart rate will be near 85% of your previously measured fitness level. Exercise duration will vary in order to expend about 400 kcal per session on supervised days and 200 kcal on unsupervised days. In addition to this training program, subjects will be provided a placebo and accelerometer as described above.

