 - Subjects will be required to wear clothes without metal on them (including zippers and bras with an underwire). If clothes have metal, we will ask that subjects change into a pair of shorts and a t-shirt or wear a lab hospital gown.
 - If there are technical issues with the DEXA machine we will measure the total amount of fat and muscle in the subjects body with the BodPod® in the IFNH.
 - We will provide a swimsuit and swim cap for subjects to wear during this procedure to help standardize the results. The swimsuit and swim cap are provided to get accurate results. Subjects will not get wet at any time during this test. Subjects will enter the device and sit down. A door will close while the subject sits in the BodPod®. They are asked to breath normal and be still. The BodPod® looks like a large white egg with a window on the door.

NOTE: in the event of scheduling conflicts, cardiovascular fitness and/or body composition assessments may be completed within 1 week of doing the OGTT during Visit 58.

END OF STUDY:

After subjects have completed Phase 5, the study will be complete.

B. Data Points

We are collecting blood and urine during experimental visits. Vital signs, including blood pressure, temperature, heart rate, as well as aerobic fitness, body composition, resting metabolism, non-exercise physical activity, appetite, as well as quality of life. Please see the study overview (Study Duration) that outlines when outcomes will be collected.

C. Study Duration

Subjects participation in this study will require about **58** study visits over about 7-8 months. Each visit will last between **1-6** hours depending on whether it is for research purposes (e.g. about 3-6 hours) or exercise training (e.g. 1-1.5 hours). There are 2 Screening Visits and 5 Test Visits. Thus, the majority of visits include exercise training (48 visits).

D. Endpoints

The primary outcome for this study will be changes of basal FMD before the insulin clamp pre and post intervention. We will also examine the influence of insulin on FMD as well as metabolic insulin sensitivity, defined as the glucose infusion during the last approximate 30 minutes of the clamp procedure. Together, these findings will help tease out vasculature vs. metabolic insulin sensitivity differences between treatments. Correlations will be conducted to understand the relationship between endothelial function and metabolic insulin sensitivity with substrate oxidation,

12/31/2499

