1.6 Study Variables

A. Independent Variables, Interventions, or Predictor Variables

This is a randomized by sex, double-blind, placebo controlled trial. A placebo is needed to minimize potential behavioral changes with pharmacological intervention. This will isolate the effects of exercise intensity based training on respective outcomes. As a result, exercise at low or high intensity with placebo will serve as standard of care/control, while exercise at low or high intensity with metformin will be the experimental conditions. Pre and post test data will be compared statistically.

Data will be analyzed using R (Vienna, Austria, 2011). A two-way repeated measures analysis of variance (ANOVA) will be used to assess time course differences (group x test). Bonferonni post-hoc analysis will be used to determine group differences and paired t-tests will be used to assess within treatment effects. Linear regression analyses will be used to identify relationships between respective variables. A *P*<0.05 will be considered statistically significant. Data will be expressed as mean ± SEM.

12/31/2499

The same statistical approach for secondary analysis will be conducted as the primary variable analysis.

B. Dependent Variables or Outcome Measures

- 1. Insulin Sensitivity
- 2. Fitness (e.g. VO2max, physical activity amount, heart rate, RPE, etc.)
- 3. Body composition (e.g. weight, fat, FFM, BMD, waist circumference, etc.)
- 4. Vascular Function (e.g. FMD, CEU, heart, arterial stiffness, etc.)
- 5. Questionnaires (e.g. Sleep, activity, quality of life, hunger, etc.)
- 6. Glucose (e.g. substrate, isotope)
- 7. Lipid Profile (e.g. TG. HDL. FFA. etc.)
- 8. Blood clinical chemistries (e.g. CBC)
- 9. C-peptide
- 10. Insulin
- 11. Inflammation (e.g. endothelin-1, adiponectin, Microparticles, etc.)
- 12. Nitrates
- 13. Gut hormones (e.g. ghrelin, GLP-1, etc.)
- 14. Pregnancy (in females), blood for screening at each admission.
- 15. Energy metabolism (e.g. rest, exercise, insulin-stimulation).
- 16. Gut microbiota
- 17. Cognitive measures using NIH toolbox

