1.9 Data Collection

A. Primary Data Collection

- Location: questionnaire data will be collected in Loree, IFNH and/or Clinical Research Center as well as at home when appropriate. Permission will be granted by the subject.
- Process of Data Collection: Research personnel approved to work on this protocol to administer and collect data. The PI will oversee the process.
- Timing and Frequency: See below for details.
- Procedures for Audio/Visual Recording: NA.
- Study Instruments: Questionnaires are widely used and routine for this type of research.
- Ethnographic Studies, Interviews, Or Observation: Paper questionnaires will be used.
- Subject Identifiers: Each specimen will be coded with a unique identifier per the study, time point collected (e.g. 0 wk, 4 wk, etc.) and test (e.g. pre or post) will also be included. No personal identifier will be used on the forms.

B. Secondary Data Collection

NA

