4.3 Number of Subjects

A. Total Number of Subjects

12/31/2499

Based on prior work by our group, we anticipate that approximately 25% of subjects who enroll in the study will withdraw/drop out early. Currently the study requires 45 people of 80 given it is a transfer project when our team was at the University of Virginia. In addition, we expect that 70% of individuals who we screen/consent will not qualify. **Thus, we expect to screen 225 subjects of whom about 67 will participate and 45 will complete the study.**

B. Total Number of Subjects If Multicenter Study

NA

C. Feasibility

We are confident that we can recruit the required number of health volunteers given the population in and surrounding Rutgers University. We are also confident we can recruit patients with risk factors for metabolic syndrome in the Clinical Academic Building at RWJMS.

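### Secondary outcomes measured three or more times need a stated model: an uncorrected repeated-measures ANOVA could exceed its 5% level under serial correlation and would normally use complete records only

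*Combined protocol and SAP*

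**What the plan says.** The inferential plan is one paragraph in Section 1.6 A: "A two-way repeated measures analysis of variance (ANOVA) will be used to assess time course differences (group x test", with Bonferroni post-hoc tests between groups, paired t-tests within groups, and significance at P<0.05. For the other outcomes it adds: "The same statistical approach for secondary analysis will be conducted as the primary variable analysis". Section 6.1 (Data Analysis), where more detail would belong, holds only the template prompt. Neither a sphericity correction nor a rule for missing values appears anywhere.

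The measurement schedule in Sections 1.3 and 1.10 goes well beyond two occasions for many secondary outcomes:

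- Diet: "Subjects will fill out a daily record of eating habits for 3 days at weeks 0, 4, 8, 12 and 16". Logs are handed out again in follow-up (Visits 57 and 58).
- Sleep and activity enjoyment: the same five weeks, and again at Visit 58, which makes six.
- Weight and waist: "Every 4 weeks subjects will have their body weight and waist circumference measured prior to a training session". Both are taken again at Visits 57 and 58.
- Accelerometry: weeks 0, 8, 16, 20 and 24 (Section 1.10).
- OGTT, treadmill fitness and body composition: pre, post and Visit 58, so three occasions.

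The primary outcome differs: "The primary outcome for this study will be changes of basal FMD before the insulin clamp pre and post intervention". No clamp is done at Visit 58, so this outcome has exactly two occasions.

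**The concern.** With more than two occasions, the ordinary F test for group by time is exact only if the covariance satisfies sphericity, meaning that all differences between occasions have equal variance. Readings taken weeks apart often correlate less the further apart they are. That violates sphericity and makes the uncorrected test reject too often.

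A second, independent matter is that classical repeated-measures ANOVA works on a complete subject-by-occasion table. A participant who misses one reading is usually left out altogether, including the readings already collected. That costs precision, and it can bias the comparison if those with gaps differ from those without. It plays no part in raising the type I error through sphericity.

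At stake are the group-by-time P values, and the population described, for the repeatedly measured secondary outcomes.

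**Working it through.** **Inputs.** Four arms of 15 (Section 1.5), nominal level 0.05 (Section 1.6 A), and five or six occasions (schedule above). Enrolment is 80, at 20 per arm (Section 1.5). Dropout is 10–15% in Section 1.5; Section 4.3 says "approximately 25% of subjects who enroll in the study will withdraw/drop out early". The plan gives no covariance and no power figure for these outcomes, so there is no figure of its own to reproduce. The covariance structures below are assumptions.

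**Step 1: size of the uncorrected test.** For k occasions the group-by-time F has 3(k−1) and (60−4)(k−1) degrees of freedom: 12 and 224 for k=5, 15 and 280 for k=6. Departure from sphericity is measured by ε = [tr(S)]² / {(k−1)·tr(S²)}, where S is the covariance of the k−1 orthonormal within-subject contrasts. ε=1 means sphericity holds. Each setting was simulated 20,000 times with no true effect; the Monte Carlo standard error near 5% is √(0.05×0.95/20,000) = 0.0015, or 0.15 points.

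| Occasions | Error structure | ε | Uncorrected | Greenhouse-Geisser |
|---|---|---|---|---|
| 2 | all structures tried | 1.00 | 4.9–5.2% | same |
| 3 | all structures tried | 0.78–1.00 | 4.7–6.6% | 4.5–5.2% |
| 5 | compound symmetry, 0.6 | 1.00 | 5.1% | 4.6% |
| 5 | AR(1), 0.5 | 0.81 | 6.5% | 4.7% |
| 5 | AR(1), 0.8 | 0.63 | 8.5% | 5.0% |
| 5 | AR(1), 0.95 | 0.55 | 9.3% | 4.8% |
| 5 | AR(1), 0.8, variance rising fourfold | 0.58 | 9.1% | 5.3% |
| 6 | compound symmetry, 0.6 | 1.00 | 4.9% | 4.3% |
| 6 | AR(1), 0.5 | 0.77 | 6.8% | 4.6% |
| 6 | AR(1), 0.8 | 0.56 | 9.3% | 4.9% |
| 6 | AR(1), 0.95 | 0.47 | 11.0% | 5.4% |
| 6 | AR(1), 0.8, variance rising fourfold | 0.52 | 10.3% | 5.2% |

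Two further simulations of the same uncorrected test under AR(1) errors gave 6.6–9.2% and 6.9–9.1% at five occasions, and 7.3–10.3% and 6.6–10.4% at six.

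**Step 2: complete records.** Dropout alone:

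- 10%: 80×0.10 = 8 lost, 72 left
- 15%: 80×0.15 = 12 lost, 68 left
- 25%: 80×0.25 = 20 lost, 60 left

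If, as an assumption, 5% of readings are also missing at each of five occasions, the complete records are 80×(1−dropout)×0.95⁵, with 0.95⁵ = 0.774. That gives 72×0.774 ≈ 56, 68×0.774 ≈ 53 and 60×0.774 ≈ 46. Scattered gaps would then cost a further 14 to 16 participants who stayed in the trial.

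**Step 3: which occasions enter.** Section 1.6 A speaks of a time course, which suggests all occasions. But its factor is called *test*, and shortly before it says "Pre and post test data will be compared statistically". Section 1.9 labels forms by "time point collected (e.g. 0 wk, 4 wk, etc.) and test (e.g. pre or post", which keeps the week apart from *test*; Section 1.8 uses *test* the same way for specimens. On that reading the model has two levels, ε is 1 by construction, and the week 4, 8 and 12 and follow-up readings have no stated analysis.

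**The case against.** The strongest reply is that the plan means pre against post throughout. Sections 1.8 and 1.9 use *test* in that sense, the paired t-tests fit it, and extending the same approach to secondary outcomes would carry the two-level comparison with it. This is a fair reading and may be the intended one. It removes the sphericity problem, but it leaves readings scheduled in every arm without an analysis, and it leaves the choice of occasions open until data are in hand.

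Four stronger conclusions that a reader might draw are not supported:

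- *The P values will be too small.* The plan is silent on correction; it does not commit to an uncorrected test. The excess also depends on the covariance: correlated readings with compound symmetry are spherical, and the level is then about 5%.
- *The plan deletes incomplete participants.* That is the usual behaviour of this method, not something the protocol states.
- *Deletion is part of why the level is liberal.* It is not; deletion affects precision and possibly bias.
- *A quarter of the 80 will be lost.* Section 1.5 pairs the 80 with 10–15% dropout. The 25% is in Section 4.3, which concerns the 45 of 80 still needed after the study's transfer.

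It is also true that these outcomes are secondary, and that a Greenhouse-Geisser correction alone would repair the level.

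**Conclusion.** The point stands as a conditional one about secondary outcomes, of low to moderate severity. If five or six occasions are analysed without correction and errors are serially correlated, a nominal 5% group-by-time test runs at roughly 6.5–9% or 6.5–11%. This rests on assumed AR(1)-type covariances with 15 per arm; under compound symmetry, or with two occasions, there is no excess. Complete-record analysis, if used, would forgo 8–12 participants at 10–15% dropout or 20 at 25%, and more if there are scattered gaps. If only pre and post are analysed, the defect is instead that interim and follow-up data have no planned use.

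A reader might extend this to the primary result. The documents do not support that: basal FMD before the clamp has two occasions, so sphericity is automatic, and there are no interim pre-clamp readings to recover.

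**What to change.** In Section 1.6 A:

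- List, for each outcome, the occasions that enter the analysis.
- For outcomes with three or more, replace the ANOVA with a linear mixed model fitted by REML, with arm, occasion and arm-by-occasion as fixed effects, unstructured covariance and Kenward-Roger degrees of freedom. Use all available observations, and state the missing-at-random assumption.
- Report the six pairwise arm contrasts in change from baseline to week 16, Bonferroni-adjusted, with confidence intervals at the matching level (1 − 0.05/6 = 99.2%).
- At a minimum, if the ANOVA is kept, apply a Greenhouse-Geisser correction. At five occasions this held the level at 4.6–5.3% in the simulations, but it does nothing for incomplete records.
- Reconcile the dropout rates in Sections 1.5 and 4.3.

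The cost is a few sentences and slightly more analysis work in R, which the plan already names; no new data are needed. The downside is the missing-at-random assumption, which the data cannot verify. An unstructured covariance also needs 5×6/2 = 15 parameters at five occasions and 6×7/2 = 21 at six, so a fallback structure should be named in advance in case the fit fails.

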1.0 Research Design

1.1 Purpose/Specific Aims

The overall purpose of the study is to test the effect of metformin on exercise intensity based training adaptations in adults with metabolic syndrome.

A. Objectives

Understand effect of metformin on training intensity mediated vascular versus metabolic insulin sensitivity in adults with metabolic syndrome for clinical health.

B. Hypotheses / Research Question(s)

The overarching hypothesis is that metformin may blunt adaptation following high intensity exercise by lowering/attenuating oxidative stress. Thus, compared with high intensity exercise plus metformin, low intensity exercise plus metformin will produce greater vascular insulin sensitivity and metabolic insulin sensitivity changes following 16 weeks of treatment. In addition, we anticipate that high intensity exercise based training alone will produce greater effects than low intensity exercise. Lastly, we hypothesize that these changes in metabolic and vascular insulin sensitivity will correlate with glycemic control and blood pressure changes.

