1.5 Sample Size Justification

The primary outcome for this study will be changes of basal flow mediated dilation (FMD) before the insulin clamp pre and post intervention. Based on our prior work 47, with 15 subjects per treatment arm we expect to have at least an 80% chance of rejecting the null hypothesis that the mean pre to post-exercise change in FMD is the same for any pair of treatments if the true means of the underlying distributions differ by more than 4.2%. Details: In computing the minimum detectable effect size of 4.2%, we assumed that the measurements for pre to post-treatment change in FMD will be normally distributed and that the measurement variability in the pre to postexercise FMD changes is the same regardless of the treatment. Moreover, we assumed that the standard deviation of the underlying distributions is 3.4% based on our prior work 47, which is notably larger than reported in the metformin literature 48. To account for a total of 6 pairwise between-treatment comparisons, a Bonferroni corrected experiment-wise type I error of 0.05 was utilized to derive the minimum detectable between-treatment difference of 4.2%. Limitations: We do not have data from the literature or from our own studies with exercise to estimate power on changes in MBV, nor with the combination of exercise+metformin. However, considering MBV, we based our estimate of sample size on our study examining the effect of insulin on MBV in both skeletal and cardiac muscle in the control setting and in the setting of elevated plasma FFA. We observed that insulin significantly increased microvascular blood volume (MBV) at both sites (p<0.01) in the absence of elevated FFA and this effect was entirely blocked by elevating plasma FFA. These observations were made in 22 subjects, although less would have yielded significance ^{36, 42}. Moreover, previous work that we conducted with HiEx+metformin demonstrated significant blunting effects on systolic blood pressure vs. exercise alone with only 8 people per group 5. Anticipated dropout: Based on our prior work with this study population, we anticipate that the study participant dropout rate will be 10-15%. Therefore, we intend to enroll 80 subjects with 20 subjects randomized to each treatment intervention.

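### Holm step-down on the same six arm pairs would keep the 0.05 family-wise error of the planned Bonferroni test, lose no rejection and sometimes gain one

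*Combined protocol and SAP*

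**What the plan says.** The four arms cross exercise intensity (LoEx, HiEx) with drug (placebo, metformin). The primary outcome is the pre-to-post change in basal FMD.

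- **Section 1.5** sizes the trial for every pair of arms: "To account for a total of 6 pairwise between-treatment comparisons, a Bonferroni corrected experiment-wise type I error of 0.05 was utilized". The null hypothesis is that "the mean pre to post-exercise change in FMD is the same for any pair of treatments". It continues: "with 15 subjects per treatment arm we expect to have at least an 80% chance of rejecting the null hypothesis" "if the true means of the underlying distributions differ by more than 4.2" (FMD percentage units), and assumes that "the standard deviation of the underlying distributions is 3.4% based on our prior work".
- **Section 1.6 A** gives the analysis: a group-by-test repeated measures ANOVA, after which "Bonferonni post-hoc analysis will be used to determine group differences". It does not list the pairs, name a primary pair or mention a stepwise version. The six-pair count comes from Section 1.5.
- **Section 1.1 B** states two explicit between-arm hypotheses. Against HiEx+metformin, "low intensity exercise plus metformin will produce greater vascular insulin sensitivity and metabolic insulin sensitivity changes following 16 weeks of treatment". High-intensity training alone is also expected to do better than low-intensity training.

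**The concern.** Single-step Bonferroni holds every pair to 0.0083, even after other pairs have been rejected. Holm relaxes the threshold once a pair has been rejected and still keeps the family-wise error at 0.05, with no extra assumption. For hypothesis tests on a fixed family, Bonferroni therefore never beats Holm.

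This matters here because the hypotheses predict more than one difference, and that is where Holm gains. The trial wants to show both that LoEx does better than HiEx under metformin and that HiEx does better than LoEx without it. The planned method makes that joint result harder to reach than family-wise control requires.

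**Working it through.** **Inputs.** From Section 1.5: 15 per arm, SD of change 3.4, difference 4.2, family-wise 0.05, six pairs. Sidedness is not stated; the equality null implies two-sided. With one pre and one post value, the group-by-test comparison is an analysis of change scores, so the pooled error has 4 × 15 − 4 = 56 df.

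**1. The plan's own figure.** Normal approximation: n = 2(z₁ + z₂)²σ²/δ², with z₁ = 2.638 (two-sided 0.0083) and z₂ = 0.842 (80% power). This gives 2 × 3.480² × 3.4²/4.2² = 15.9, so 16 per arm against the stated 15. At 15 per arm the same approximation gives 77.2% power. The stated design is thus roughly reproduced. How well the 80% holds is a separate matter.

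**2. Bonferroni, pooled t.** SE = 3.4 × √(2/15) = 1.2415. Noncentrality = 4.2/1.2415 = 3.383. Critical value 2.735. Power for one pair = 73.9%.

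**3. Holm.** Order the six p-values and compare them in turn with 0.05/6 = 0.0083, 0.05/5 = 0.0100, 0.05/4 = 0.0125, 0.05/3 = 0.0167, 0.05/2 = 0.025 and 0.05, stopping at the first failure. The first threshold is Bonferroni's, so the chance of at least one rejection is identical. Later thresholds are looser, so nothing is lost. The gain for a pair depends on how many other pairs are rejected before it.

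**4. Size of the gain.** Simulation, 200,000 trials per pattern, 15 per arm. Power is for LoEx+metformin vs HiEx+metformin, where the true difference is 4.2 throughout.

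| True mean change: LoEx+placebo / HiEx+placebo / LoEx+metformin / HiEx+metformin | Bonferroni | Holm |
|---|---|---|
| 2.1 / 2.1 / 4.2 / 0 (other arms midway) | 73.9% | 74.4% |
| 4.2 / 4.2 / 4.2 / 0 (only HiEx+metformin differs) | 73.9% | 76.8% |
| 0 / 4.2 / 4.2 / 0 (all four single-factor pairs differ) | 73.9% | 79.0% |

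The gain is 0.5 to 5.1 points. The third pattern is closest to Section 1.1 B. Under it, the chance of rejecting both explicit hypotheses (LoEx+metformin vs HiEx+metformin, and HiEx+placebo vs LoEx+placebo) is about 55% with Bonferroni and about 65% with Holm. With all four means equal, the family-wise error is 4.0% under both.

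**5. Completers.** Section 1.5 enrols 20 per arm and expects 10–15% dropout: 20 × 0.85 = 17 to 20 × 0.90 = 18 completers. Bonferroni power for a pair is then 80.6% to 83.5%. Section 4.3 A expects about 25% dropout: 20 × 0.75 = 15 completers, and 73.9%.

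**The case against.** **Bonferroni is valid, prespecified and matches the sizing.** This stands. Nothing in the plan inflates the type I error, and the sponsor may keep the method.

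**The gain can be negligible.** This stands in part. With the other arms midway it is half a point. Tukey on six pairs gives 76.6% whatever the other arms do, so it does better than Holm in that pattern and worse in the third. Holm's advantage is largest where several predicted differences are real.

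**Stronger readings that the documents do not support:**

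- *That the family should be cut to the four single-factor pairs at no cost.* The two diagonal pairs (LoEx+placebo vs HiEx+metformin, HiEx+placebo vs LoEx+metformin) match no formal hypothesis. Bonferroni on four pairs would give 78.5%. But Section 1.5 powers any pair, and Section 1.2 gives a rationale for one diagonal: it presents high-intensity exercise as established treatment, and low-intensity exercise as an alternative on which to test what metformin adds. Cutting the family gives up confirmatory claims on both diagonals. If only one arm differs, the chance of at least one rejection falls from about 91.5% to 90.2%.
- *That a primary comparison loses power.* The plan names a primary outcome but no primary pair.
- *That Holm recovers unused alpha.* When all arms are equal, its error is the same 4.0%. It differs from Bonferroni only after a first rejection.
- *That Bonferroni leaves the trial underpowered.* With the dropout rate in Section 1.5 it exceeds 80%. A shortfall appears at 15 completers, the number implied by the rate in Section 4.3 A.

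**Conclusion.** The point holds as a cheap improvement. On the six pairs that the plan already tests, Holm gives the same family-wise protection, loses no rejection and adds 0.5 to 5.1 points of power for a given pair at 15 per arm. It adds about 10 points to the chance of confirming both explicit hypotheses if all four single-factor differences are 4.2.

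These sizes rest on the plan's SD of 3.4 and difference of 4.2, two-sided tests, equal variances, 15 completers per arm, the assumed patterns of means, and reading the hypotheses on the FMD change. That Holm never rejects less than Bonferroni depends on none of these.

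**What to change.** In Section 1.6 A, replace the Bonferroni post-hoc wording with: *Holm step-down over the six pairwise comparisons at family-wise 0.05.* List the six pairs there, so that the family does not have to be inferred from Section 1.5. Section 1.6 applies the same approach to secondary outcomes, so state whether the change carries over to them.

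The change should be dated and documented before unblinding. Section 4.3 A describes a transferred project with 45 of 80 participants still required, so the record should show that no treatment comparison informed it.

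Cost: wording and documentation only; no participants, visits or procedures change. Holm has no simple matching simultaneous intervals. Tukey intervals can be reported alongside; they are about 3% narrower than Bonferroni intervals (2.648/2.735 = 0.968). The plan should say that Holm decides significance, since the two can disagree on a borderline pair.

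Restricting the confirmatory family to the four single-factor pairs is the sponsor's option. If chosen, it should be justified and fixed before unblinding, with the diagonal pairs reported descriptively.
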